2.2 Aim and Objectives

2.2.1 Aim

This study will compare quality of recovery between desflurane and isoflurane inhalational anaesthesia.

2.2.2 Primary Objective and Hypothesis

The primary objective of the study is to evaluate whether there is a difference between post-operative quality of recovery in patients who received desflurane and in patients who received isoflurane for maintenance of anaesthesia, using the QoR-15 score, a patient-rated outcome measure.

Isoflurane is the standard drug used in our setting for maintenance of anaesthesia and will therefore be used as the drug for the control group. Desflurane will be used as the interventional drug.

The minimal clinically important difference for the post-operative QoR-15 has been found to be 8. In other words, an intervention that changes the mean post-operative score by 8, can be interpreted to signify a clinically important improvement or deterioration.

The null hypothesis for this study is that there is no statistically significant difference in mean post-operative QoR-15 scores of patients receiving isoflurane and desflurane for maintenance of anaesthesia. The alternative hypothesis is that there is a statistically significant difference in mean post-operative QoR-15 scores between patients receiving isoflurane and desflurane.

2.2.3 Secondary Objectives

A secondary objective will be to compare the consumption and relative cost of using isoflurane vs desflurane with a minimal (0.25-0.5 ml/min) or basal (0.2-0.25 ml/min) flow anaesthetic technique. This will be done by comparing the amount of vapour used in millilitre per hour between desflurane and isoflurane during minimal or basal flow anaesthesia. The relative cost of the vapour used will be estimated, based on the current government purchase price of isoflurane and desflurane.

Furthermore, the difference in time spent in recovery between the two patient groups will also be compared.

3 Methodology

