 - Should the bag on the anaesthetic machine collapse during minimal or basal flow anaesthesia (e.g. because of a poor seal from the LMA, or due to circuit leak) the following steps should be taken: increase the fresh gas flow to 2 L/min and adjust the vaporiser concentration to maintain 1MAC, allow the bellows to fill and then return to the previous concentration and fresh gas flow settings.
 - Desflurane:

- After the airway is secured, fresh gas flow is reduced to 2 l/min and the desflurane vaporiser is opened to 12%. This is maintained until 1MAC is reached, usually about 3-5 minutes.
- The fresh gas flow will then be turned down to 0.2-0.5 l/min and the vaporiser adjusted to maintain 1MAC. The aim will be to reduce the fresh gas flow as low as possible, taking into consideration the amount of machine and/or circuit leak.
- If basal flow (0.2L/min) is reached, FiO₂ will be set to 100% to meet the patient's oxygen demand.
- Should the bag on the anaesthetic machine collapse during minimal or basal flow anaesthesia (e.g. because of a poor seal from the LMA, or due to circuit leak) the following steps should be taken: turn the vaporiser concentration to 12% and the fresh gas flow to 2 L/min, allow the bellows to fill and then return to the previous concentration and fresh gas flow settings.
- The use of minimal or basal fresh gas flow is intentional, to minimise the amount of anaesthetic vapour used. When basal flow is used, 100% oxygen is required to meet patient's oxygen demand.
- Managing Potential Problems:
 - Should the ophthalmologist complain that the patient is in too light a plane of anaesthesia, the patient may be deepened with a bolus of Propofol 0.5-1 mg/kg.
 - For intra-operative analgesia (for example if patient develops tachycardia or hypertension), administer 50mcg Fentanyl boluses intravenously.
 - When post-operative analgesia is required, administer 50-100mg of Tramadol intravenously as a bolus 20 minutes before the end of the procedure.
 - For post-operative nausea or vomiting (only if required), administer 4mg of Ondansetron intravenously as a bolus, followed by 10mg of Metoclopramide after 30 minutes (only if further treatment is required).
- End of Procedure:
 - If a small dose of muscle relaxant was used, the effects should be reversed with Neostigmine 0.04mg/kg (2-3mg for most adults) 10-20 minutes before the end of the procedure. Glycopyrrolate or Atropine may be added to prevent bradycardia and gastro-intestinal side-effects.

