3.2.6 Outcomes

Primary outcome measures:

- Quality of recovery will be assessed in all participants with the QoR-15 score.
 - A baseline QoR-15 will be measured pre-operatively, and a repeat measurement will be done on day 1 post-operatively before discharge.
 - For each patient, the pre- and post-operative QoR-15 scores will be recorded, as well as the difference between the two measurements. The mean and median differences between the pre- and post-operative QoR-15 scores of the control group and the intervention group will be compared and tested for significance.
 - The mean and median post-operative QoR-15 scores of the control group and the intervention group will be compared and tested for significance.

[figure not shown]
Secondary outcome measures:

- To evaluate the consumption and cost of isoflurane and desflurane with a minimal or basal anaesthetic technique:
 - The vapour use per case in millilitres will be recorded from the anaesthetic machine.
 - The purchase price for isoflurane and desflurane will be obtained from the pharmacy.
 - The mean and median consumption of vapour between the two groups will be compared.
 - The mean and median cost of isoflurane and desflurane will be compared.

- To evaluate time in recovery:
 - The time the patient enters and leaves the recovery room will be recorded, as well as the total time the patient spends in the recovery room.
 - The mean and median time spent in recovery will be compared between the two groups.

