3.6 Data Analysis & Statistical Methods

Demographic and clinical characteristics of patients will be summarised descriptively. Continuous variables (e.g. age or weight) will be summarised by mean, standard deviation, median, interquartile range, minimum and maximum values. Categorical variables (e.g. ethnicity or ASA status), will be summarised by frequency count and percentage calculations.

QoR scores will be considered as a continuous variable and will be summarised as above per treatment group (desflurane and isoflurane).

The null hypothesis for this study is that there is no statistically significant difference in mean post-operative QoR-15 scores of patients receiving isoflurane and desflurane for maintenance of anaesthesia. The alternative hypothesis is that there is a statistically significant difference in mean post-operative QoR-15 scores between patients receiving isoflurane and desflurane.

Based on the available literature, it is assumed that the quality of recovery scores will follow a normal distribution. The data will be inspected for normality prior to analysis.

For the primary objective, the mean and median difference in post-operative QoR-15 scores between the two groups will be tested for significance by the two-sided two-sample t-test and the nonparametric Wilcoxon rank sum test respectively. The mean and median difference between the pre-operative and post-operative QoR-15 scores for the two groups will also be tested for significance by the two-sided two-sample t-test and the nonparametric Wilcoxon rank sum test respectively.

For the secondary objectives, mean and median difference in consumption of vapour and time spent in recovery will be tested for significance by the t-test and Wilcoxon test as above.

Analysis, or comparisons, of subgroups of patients may be performed if it would be of clinical interest; for example, if there appears to be a significant difference in QoR scores between male and female patients.

Results will be presented in tables and graphs or verbatim, as applicable.

All statistical analyses will be performed on SAS (SAS institute Inc, Carey, NC, USA), Release 9.4 or higher, running under Microsoft Windows for a personal computer. Statistical tests will be two-sided and p values ≤ 0.05 (5%) will be considered significant.

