6. Airway management with a Laryngeal Mask Airway (LMA), size selected according to patient weight.

Use of Muscle Relaxants During Procedure:

If required, a small dose of muscle relaxant may be administered to facilitate immobility during the procedure. For Rocuronium, a dose of up to 0.15mg/kg may be used (about 10-15mg for most adults). For Cisatracurium, a dose of up to 0.05mg/kg may be used (about 2.5 - 4mg for most adults). Top-up doses may be given every 30-40 minutes, if required; dosing should be the same as the initial dose. Ensure reversal of the muscle relaxant with Neostigmine 10-20 minutes before the end of the procedure.

Isoflurane Group: Maintenance of Anaesthesia:

1. Once the airway is secured, reduce fresh gas flow to 2 l/min.
2. Open the Isoflurane vapouriser and adjust to attain 1MAC.
3. Once 1MAC is attained, reduce fresh gas flow to 0.2-0.5 l/min. Aim to reduce the fresh gas flow as low as possible, taking into consideration the machine leak.
4. Adjust the vapouriser to maintain 1MAC throughout the procedure.
5. If basal flow (0.2l/min) is reached, ensure that FiO₂ is 100% to meet the patient's oxygen demand.
6. Should the bellows on the anaesthetic machine collapse during basal or minimal flow anaesthesia, take the following steps: Increase the FGF to 2 l/min and adjust the vapouriser concentration to maintain 1MAC. Continue like this until the bellows are filled, then return to the previous setting in concentration and FGF.

Desflurane Group: Maintenance of Anaesthesia:

1. Once the airway is secured, reduce fresh gas flow to 2 l/min.
2. Open the Desflurane vapouriser to 12%.
3. Maintain these settings until 1MAC is reached, about 3-5 minutes.
4. Once 1MAC is attained, reduce fresh gas flow to 0.2-0.5 l/min. Aim to reduce the fresh gas flow as low as possible, taking into consideration the machine leak.
5. Slowly adjust the vapouriser concentration to maintain 1MAC throughout the procedure (usually 8-10%).
6. If basal flow (0.2l/min) is reached, ensure that FiO₂ is 100% to meet the patient's oxygen demand.
7. Should the bellows on the anaesthetic machine collapse during basal flow or minimal flow anaesthesia, take the following steps: Turn the vapouriser concentration back to 12%, then increase the FGF to 2 l/min. Continue like this until the bellows are filled, then return to the previous setting in concentration and FGF.

End of Procedure:

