6.7 Case Report Form: Data Collection

Case Report Form: Data Collection				
Date: ___ / ___ / ___		Study #: _____		
SECTION A: PATIENT INFORMATION:				
Age:	years			
Gender:	Male	Female		
Weight:	kg	Height:	m	BMI: _____
ASA Status:	I	II	III	IV
Risk for PONV:	Female	Previous PONV	Motion Sickness	Non-smoker
Smoking History:	Non-smoker	Ex-smoker	Current Smoker	Pack years: _____
Comorbidities:	None	Hypertension	Diabetes	Pulmonary Disease
	Cerebrovascular Disease	Renal Disease	HIV	Cardiovascular Disease Psychiatric Conditions Other (Specify below)
If Other, Details of Condition: _____				
Any Anaesthesia in the Past Month?		Yes	No	
If YES:		General	Regional	Local Infiltration
Any Complications?		Yes	No	
If YES, Describe: _____				
SECTION B: INFORMATION ABOUT PROCEDURE:				
Group:	Desflurane	Isoflurane		
Intravenous Induction Time:	End of Anaesthesia: _____			
Time Vapour Started:	Time Vapour Stopped: _____			
Millilitres of Vapour Used:	ml			
Propofol at Induction:	mg			
Fentanyl at Induction:	mcg			
Intra-op Propofol Top-up:	No	Yes →	Number of top-ups given: _____ Total top-up dose: _____ mg	
Intra-op Fentanyl Top-up:	No	Yes →	Number of top-ups given: _____ Total top-up dose: _____ mcg	
Intra-op Muscle Relax. Top-up:	No	Yes →	Number of top-ups given: _____ Total top-up dose: _____ mg	
Neostigmine given:	No	Yes →	Time: _____ Dose: _____ mg	
Atropine / Glycopyrrolate given:	No	Yes →	Time: _____ Dose: _____ mg	
Intra- or Post-op Tramadol:	No	Yes →	Time: _____ Dose: _____ mg	
Post-Op Ondansetron:	No	Yes →	Time: _____ Dose: _____ mg	
Post-Op Metoclopramide:	No	Yes →	Time: _____ Dose: _____ mg	
Adverse events:	Bronchospasm	Laryngospasm	Nausea / Vomiting	Other (specify below)
Please inform [name] immediately of any adverse events ([name])				
Time into Recovery:			Time out of Recovery: _____	
Anaesthesia administered as per study protocol:			Yes	No
If no, please describe modification: _____				
[name]; MMed Research; Feb 2020			DIQoR Trial	

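### The consumption objective is ml per hour at minimal or basal flow, but the plan tests total ml per case and the data form cannot separate the 2 l/min wash-in

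*Combined protocol and SAP*

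**What the plan says.** Section 2.2.3 sets the consumption comparison as "comparing the amount of vapour used in millilitre per hour between desflurane and isoflurane during minimal or basal flow anaesthesia", and describes the technique as "minimal (0.25-0.5 ml/min) or basal (0.2-0.25 ml/min) flow anaesthetic technique".

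Section 3.2.6 describes the measurement differently: "The vapour use per case in millilitres will be recorded from the anaesthetic machine". It continues: "The mean and median consumption of vapour between the two groups will be compared". Section 3.6 says that "mean and median difference in consumption of vapour and time spent in recovery will be tested for significance by the t-test and Wilcoxon test". Neither section mentions hours, a denominator or a phase of the anaesthetic.

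Form 6.7 has one volume field, "Millilitres of Vapour Used", and the times at which vapour was started and stopped. It has no field for fresh gas flow, for the time flow was first reduced, or for the millilitres used by then. Section 3.4.1 lists the workstation's stored history as a source for vapour consumption and anaesthesia times, without saying whether consumption is time-stamped.

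Sections 3.2.3 and 6.6 fix the order of steps. In the desflurane arm, "After the airway is secured, fresh gas flow is reduced to 2 l/min and the desflurane vaporiser is opened to 12" per cent, and this is held until 1 MAC, usually about 3-5 minutes. Flow then falls to 0.2-0.5 l/min. Isoflurane follows the same flows, but the vaporiser is simply adjusted to reach 1 MAC, with no setting and no time. If the bag collapses, flow returns to 2 l/min in both arms until it refills.

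**The concern.** Followed as written, the plan tests a different quantity from the one the objective names. A per-case total has no time base. It also contains the wash-in, and any refills, at 2 l/min. A whole-case ml/h can be derived from form 6.7, but the rate at minimal or basal flow cannot.

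Wash-in is a front-loaded amount that does not grow with the length of the case. Dividing the total by vapour time therefore gives a rate that depends on how long cases last in this theatre. A reader who takes the reported figure as the running rate at low flow, and applies it to other case lengths, would overstate use in longer cases and understate it in shorter ones. The cost comparison in 2.2.3 rests on the same measurement.

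Separately, the flow bands in 2.2.3 are in ml/min, while 3.2.3 and 6.6 use l/min, a 1000-fold difference within the document.

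**Working it through.** **Plan's own figure.** The documents give no expected figure for vapour consumption. The only calculated design figure is 85 per group in 3.2.8. It reproduces (t-test: 84.9, rounded up to 85; power 80.0%) but does not bear on this point.

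**Inputs for desflurane.**
- Wash-in: 2 l/min at 12% for about 3-5 min (3.2.3, 6.6).
- After the switch: 0.2-0.5 l/min (3.2.3, 6.6) at a usual setting of 8-10% (6.6).
- Case length: mean 74 min, range 20-180 min, with 141 of 166 cases (85%) at 40-120 min (3.2.1). These are surgery times, used here as a stand-in for vapour time.

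**Formula.** Vapour per minute = fresh gas flow × vaporiser setting. Let w be wash-in minutes, T vapour time in minutes, and R the wash-in rate divided by the low-flow rate. Then

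whole-case rate / low-flow rate = 1 + (w/T) × (R − 1).

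The conversion from vapour to liquid millilitres cancels.

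**Rates.** Wash-in: 2000 ml/min × 0.12 = 240 ml vapour/min. Low flow: from 200 × 0.08 = 16 to 500 × 0.10 = 50 ml vapour/min. So R runs from 240/50 = 4.8 to 240/16 = 15. Middle case: 350 × 0.09 = 31.5, giving R = 7.62.

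**Whole-case rate as a multiple of the low-flow rate.**

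| Vapour time | Low contrast (w 3, R 4.8) | Middle (w 4, R 7.62) | High contrast (w 5, R 15) | Wash-in share, middle |
|---|---|---|---|---|
| 20 min | 1.570 | 2.324 | 4.500 | 66% |
| 40 min | 1.285 | 1.662 | 2.750 | 46% |
| 74 min | 1.154 | 1.358 | 1.946 | 30% |
| 120 min | 1.095 | 1.221 | 1.583 | 21% |
| 180 min | 1.063 | 1.147 | 1.389 | 15% |

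Middle case at 74 min: 1 + (4/74) × 6.62 = 1.358, an excess of 36% (range 15-95%).

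**Dependence on case length.** From 120 to 40 min the whole-case rate rises by 1.662/1.221 − 1 = 36% in the middle case. At the extremes the rise is 1.285/1.095 − 1 = 17% and 2.750/1.583 − 1 = 74%.

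**Sensitivity.** Replacing setting C by C/(1 − C), to allow for carrier gas, gives multiples of 1.16-1.99 at 74 min, almost the same.

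**Isoflurane.** The documents give no vaporiser setting in either phase and no wash-in time. If one assumes an equal setting in both phases (R = 2/0.5 = 4 to 2/0.2 = 10) and 3-5 min of wash-in, the multiple at 74 min is 1.12-1.61. This is an assumption, not a protocol figure.

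**The case against.** The strongest reply is that 2.2.3 can be read as naming a technique rather than a phase. The technique as protocolled begins at 2 l/min in both arms, so wash-in belongs to it, and the per-case total in 3.2.6 would be the intended measure. Section 2.2.3 also costs the vapour used, and wash-in is part of that. This reading is tenable. Against it, 3.2.3 uses the same term for the period in which the bag may collapse after flow has been reduced, which fits the phase reading. The text is ambiguous, and on either reading the per-hour step is absent from 3.2.6 and 3.6.

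A reader might infer that the hourly figure climbs steeply as cases shorten. The large excess (132% in the middle case) belongs to a 20-minute case, the shortest in the theatre review. Across 40-120 minutes, where 85% of cases lie, the change is moderate.

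A reader might also infer that the comparison between arms is biased. The documents do not show this. Randomisation balances case length in expectation, and inflation common to both arms cancels in the ratio. Under the equal-setting assumption for isoflurane, with 4 min of wash-in and 0.35 l/min, R = 2/0.35 = 5.71 and its multiple at 74 min is 1.25 against 1.36 for desflurane, a shift in the ratio of about 8% (about 6% at 120 min, 13% at 40 min). Other isoflurane settings could make this smaller or larger.

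Finally, this is a secondary outcome and does not touch the QoR-15 analysis. That stands.

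**Conclusion.** The mismatch holds on the text: the objective is a rate at minimal or basal flow, the planned test is on per-case consumption, and form 6.7 cannot supply the low-flow rate. For desflurane the gap between whole-case and low-flow ml/h is large enough to need a definition before analysis, at about 36% in a case of average length (15-95%).

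The size rests on four assumptions. The machine total includes the wash-in, which follows from its being a per-case figure and from the order of steps but is not stated. Surgery duration stands in for vapour time. Settings are constant within each phase, and the l/min flows of 3.2.3 and 6.6 are used. Bag-collapse refills are ignored; they would add to the excess.

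The conclusion is an undefined measure that depends on case mix. It is not a demonstrated bias between arms: how far the desflurane/isoflurane ratio of whole-case rates departs from the low-flow ratio cannot be determined from the documents.

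**What to change.** 1. In 2.2.3, 3.2.6 and 3.6, define the main consumption outcome, for all randomised cases, as whole-case millilitres divided by hours from vapour start to vapour stop. Both items are already on form 6.7. Report whole-case ml and cost alongside. Describe the outcome as the whole technique including wash-in, and say that the rate depends on case length.

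2. To answer the low-flow question, add two entries to Section B of form 6.7: the clock time and the machine's cumulative millilitres when flow is first reduced to the low-flow range. If the workstation history proves to be time-stamped, take them from there, which could also recover cases already done.

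3. Report the post-switch rate, (final ml − ml at switch) / hours from switch to vapour stop, as a supportive measure only. State that it includes bellows refills at 2 l/min, how many cases never reached low flow, and how many earlier cases lack the reading. It should not be the main outcome, because leaving out cases that never reached low flow selects on an event after randomisation.

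4. Reconcile the ml/min flow bands in 2.2.3 with the l/min values in 3.2.3 and 6.6.

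Items 1 and 4 cost only wording. Item 2 costs one extra reading per case by the anaesthetist. New fields cannot supply readings for patients already treated: the latest revision is dated 19 April 2021, and collection had resumed in October 2020 and was due to end in July 2021 (1.2, 1.5).

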3.1 Trial Design

This study will be conducted as a randomised, controlled, patient and observer blinded, single-centre trial with two parallel groups and a primary end-point of 15-point Quality of Recovery Score on day 1 after surgery. Randomization will be performed as block randomization with a 1:1 allocation.

3.2 Participants, Interventions and Outcomes

3.2.1 Study Setting

The study will be conducted in the theatre complex at [name] Academic Hospital, a tertiary training centre affiliated with Sefako Makgatho Health Sciences University. Specifically, the study will be conducted in the ophthalmological theatre, on patients undergoing ophthalmological surgery under general anaesthetic.

The decision to use patients for ophthalmological surgery is based on the consideration that the procedures last an average of 1 hour, the patients are usually systemically well, the anaesthetic technique can be standardised for all patients, the surgery itself is unlikely to lead to poor quality of recovery and the patients are unlikely to require high doses of opioids for analgesia. Review of the theatre records for the ophthalmology theatre revealed that 166

patients between the ages of 18-87 years underwent general anaesthesia in the 6 months between 1 March – 31 August 2018. Mean age was 42 years, with 150 patients in the age range 18-65 years. Mean duration of surgery was 74 minutes (range: 20-180 minutes), with 141 cases lasting 40-120 minutes.

3.2.2 Eligibility Criteria

Inclusion Criteria:

- Adult patients between the ages of 18-80 years of age.
- Patients presenting for ophthalmological surgery under general anaesthesia.
- ASA I and II.
- Able to communicate in English, Setswana or Afrikaans.

Exclusion Criteria:

- Patients outside the specified age range.
- ASA III and above.
- Patients with contra-indications to Laryngeal Mask Airway use during general anaesthesia.
- Patients with severe medical or surgical conditions, who are expected to have prolonged admissions or ICU admissions.
- Patients with uncontrolled psychiatric conditions like depression, schizophrenia, mania, dementia.
- Patients with known allergy or adverse reaction to volatile anaesthetics.
- Patients with known or suspected susceptibility to Malignant Hyperthermia.
- Patients with incomplete records (Data Collection Form and QoR-15).

